Methodology: This is a randomised, phase III, multicentre, double-blind, placebo-controlled efficacy and safety study of oral darolutamide in patients with nmCRPC who are at high risk for developing metastatic disease. The study has a design of 2 parallel groups and consists of 2 periods: a study treatment period and a follow-up period. All eligible patients will be randomised to receive darolutamide 600 mg twice daily or placebo in a 2:1 ratio in a double-blind manner. Randomisation will be stratified by PSA doubling time (PSADT; ≤ 6 months vs. > 6 months) and use of osteoclast-targeted therapy (yes vs. no). All patients will visit the study centre at day 1, day 15, day 29, week 16, and every 16 weeks thereafter. CT/MRI and bone scans will be obtained at baseline and every 16 weeks until metastasis. Absence or presence of metastasis will be confirmed at baseline and during the double-blind treatment phase by a blinded independent central reading. Changes identified by central reading must be confirmed with anatomic imaging (CT/MRI or x-ray). Upon central confirmation of metastasis, the patient must be withdrawn from the study treatment and the patient will be followed every 16 weeks for secondary and additional variables (OS, first SSE, pain progression, first prostate cancer-related invasive procedure, initiation of subsequent antineoplastic therapy, initiation of cytotoxic chemotherapy, initiation of opioid use for pain, and changes in ECOG performance status and QoL) until the end of the study by visit or telephone contact. Patients initiating a prohibited therapy before confirmation of the metastasis during the double-blind part should discontinue study treatment and patients will be followed only for survival status until the end of the study. The double-blind part is planned to be continued until the total number of MFS events have been reached at approximately 385 events.		

Once the study results are available, and if they support a positive benefit/risk assessment for darolutamide in the study by judgment of the Sponsor (considering feedback from the study steering committee and/or health authorities), those patients who are on study treatment (darolutamide or placebo) will be offered the opportunity to receive darolutamide through open-label treatment in this study.

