5.7 Prior, concomitant and follow-up treatments

5.7.1 Prior and concomitant treatments

History of all prostate cancer treatments, including radiotherapy, before the time of IC must be recorded on the CRFs.

All concomitant treatments from the time of IC until the end-of-study treatment visit must be recorded on the CRFs. Contrast media do not need to be recorded as concomitant medication unless there is an adverse event related to its administration (e.g. allergic reaction). Once the patient has been withdrawn from study treatment, follow-up treatments will be recorded if used to treat new related or unresolved related AEs or if it is a systemic antineoplastic therapy.

Patients who have not undergone bilateral orchiectomy must continue GnRH agonist or antagonist therapy during the study.

The patient must not have been administered another investigational drug within 28 days before randomisation.

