Collection of AEs and SAEs considered to be related to study treatment or procedures	X	X	X ⁵	X ⁵
Collection of concomitant treatments used to treat new related or unresolved related AEs	X	X	X	X
Darolutamide dispensing and accountability			X	X ⁷
First SSE	X	X	X	X
First prostate cancer-related invasive procedure for prostate cancer	X	X	X	X
Survival status ⁸	X	X	X	X
Serum PSA	X		X ⁶	
Chest, abdomen, and pelvic CT/MRI	X		X ⁶	
Bone scan ⁴	X		X ⁶	

Abbreviations: ECOG = Eastern Cooperative Oncology Group; EOS = end-of-study; PSA = prostate-specific antigen; SSE = symptomatic skeletal event

* Note: In case a patient initiates a prohibited treatment during the open-label treatment phase before metastasis confirmed by local reading, the patient must discontinue study treatment and will be followed for survival until the end of the study (see Section 4.7.1 for additional details).

¹ Until metastasis, death, transition to a roll-over study, or the end of the study

² Until death or the end of the study

³ Patients will be instructed to complete the diary for 6 days before each 16-week visit until documented pain progression. Pain medications will be recorded on CRFs at each 16-week visit until documented pain progression.

⁴ New lesion(s) in bone scan must be confirmed by CT/MRI (whichever imaging was conducted at screening for soft tissue) or x-ray. If confirmatory scan is negative (does not confirm progression), the patient will continue to visit study centre as specified in the study event table.

- ⁵ For placebo patients crossing over to open-label darolutamide, all AEs and SAEs irrespective of relatedness will be captured.
- ⁶ Placebo patients crossing over to open-label darolutamide will have central PSA testing and local imaging, radiology .
- ⁷ Only drug accountability performed at the end-of-study treatment visit.
- ⁸ Survival data will also be collected through an additional survival sweep. All patients considered alive shortly after the database cut-off date for the MFS analysis and prior to any subsequent analysis of OS will be contacted for survival status.

Patients initiating a prohibited treatment before confirmed metastasis will be followed only for survival status every 16 weeks until the end of the study.

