6.3.2.4 Time to pain progression

Pain progression is defined as an increase of ≥ 2 points from baseline (day 1 score) in question 3 of BPI-SF (related to the worst pain in the last 24 hours) taken as a 7-day average, or initiation of short or long-acting opioids for pain, whichever comes first.

Pain will be assessed with the BPI-SF questionnaire (Appendix 4) during the visit, pain diary entries from 6 days preceding the visit and opioid use from baseline until documented pain progression. The pain diary consists of 6 copies of BPI-SF questionnaire.

Initiation or change in the use of other non-opioid analgesics is not used in the analysis of pain progression.

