### **6.1.4 Prior and concomitant medications**

Concomitant medications and procedures are:

- Prior prostate cancer therapy: frequency of patients for each drug category
- Radiotherapy (prior)
- Opioid treatment (prior, concurrent, and follow-up): frequency of patients – patient listings
- Diagnostic and therapeutic procedures: frequency of patients by procedure (prior, concurrent)
- Concomitant medications: frequency of patients for each drug category
- Concomitant statin medications: frequency of patients
- Diagnostic and therapeutic procedures related to AE: frequency of patients by procedure (concurrent)

The dictionary used for coding medications is the WHO Drug dictionary.

In addition to the FAS population, concomitant medication will also be summarized on the SAF population.

For selection of statins medications, please refer to Appendix 9.9.

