**Table 19: Censoring Rules for Time to first opioid for cancer pain**

Situation	End Date on or prior to cut-off date	Censored
Recorded opioid use for cancer pain during the study	Date of first opioid use	No
No opioid use for cancer pain during study	Date of last visit	Yes
Patient has no post baseline assessment at data cut-off	Date of randomization	Yes

This endpoint is selected from the ADTTE dataset using variable PARAMCD equal to ‘OCP’.

A log rank test stratified by same stratification factors used in the MFS analysis will be used to compare the darolutamide and placebo groups.

The hazard ratio as well as its 95% CI will be generated with a Cox regression model as for MFS.

Kaplan-Meier survival curves (product-limit estimates) will be presented by treatment arm. Kaplan-Meier estimates of the median time and first and third quartiles times will be presented with 95% CIs.

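### Time to first opioid use censors at the last visit, although off study drug opioid use need only be recorded until documented pain progression

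*Protocol*

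**What the plan says.** **Collection on study drug.** Protocol 5.7.1: "All concomitant treatments from the time of IC until the end-of-study treatment visit must be recorded on the CRFs".

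**Collection off study drug.** The same section then narrows: "follow-up treatments will be recorded if used to treat new related or unresolved related AEs or if it is a systemic antineoplastic therapy". Table 4 has a separate row for pain medications, limited by footnote 3: "Pain medications will be recorded on CRFs at each 16-week visit until documented pain progression". The follow-up schedule in SAP Appendix 9.1 repeats this stop. Protocol 6.3.2.4 sets the same window for the pain endpoint: "opioid use from baseline until documented pain progression".

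**Pain progression.** Protocol 6.3.2.4 defines it as a rise of at least 2 points on BPI-SF question 3, "or initiation of short or long-acting opioids for pain, whichever comes first".

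**The opioid endpoint.** SAP 6.2.3.8 adds time from randomization to first opioid use for cancer pain, with no stop at pain progression. In Table 19 the row "No opioid use for cancer pain during study" is censored at the date of the last visit. SAP Appendix 9.10 takes the events from the concomitant medication dataset (ATC N02A).

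**Text pointing the other way.** The Synopsis (Methodology) lists "initiation of opioid use for pain" among items followed until the end of the study. Protocol 6.1.3 lists pain medications among the items captured at follow-up contacts and gives no stopping point. SAP 6.1.4 plans a table of "Opioid treatment (prior, concurrent, and follow-up): frequency of patients".

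**The concern.** Censoring a man at a given date asserts that he was observed to be event-free until then. Table 19 makes that assertion up to the last visit, while the schedule requires opioid data off study drug only until documented pain progression. Stopping there suits the composite pain endpoint, which is complete at that moment. It does not suit a separate opioid endpoint, because men who have just progressed on BPI-SF are plausibly those most likely to start an opioid next.

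Two outputs are at stake: the estimate for time to first opioid use, and the follow-up part of the opioid frequency table. Loss requires both being off study drug and having progressed on BPI-SF. If darolutamide delays both, the loss is heavier on placebo and the comparison is distorted.

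**Working it through.** **1. Collection against censoring.** The documents give no figure for this endpoint, so the check starts by setting the rules side by side.

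| State of the man | Opioid record required by 5.7.1? | Required by Table 4, footnote 3? | At risk under Table 19? |
|---|---|---|---|
| On drug, no pain progression | Yes | Not needed | Yes |
| On drug, after BPI-SF progression | Yes | Not needed | Yes |
| Off drug, no pain progression | No | Yes | Yes |
| Off drug, after BPI-SF progression | No | No | Yes |

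Only the last row fails. Contacts in that state continue every 16 weeks until death or end of study (Protocol 6.1.3), so the last visit can fall long after the duty to record opioids has ended. Placebo men who cross over are ambiguous: Table 4 applies footnote 3 to them, while 5.7.1 requires all concomitant treatments until the end-of-study treatment visit.

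**2. The SAP's own practice elsewhere.** Table 11 (cytotoxic chemotherapy) censors at the last visit at which the question was collected. Tables 15 and 16 do the same, except that their lost-to-follow-up rows add a data cut-off alternative. Table 19 lacks this condition.

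**3. Direction.** Let E be true first opioid starts in an arm, L the share lost, T the true time at risk and X the extra time credited as opioid-free. The observed rate is E(1 − L)/(T + X). The darolutamide/placebo rate ratio is therefore multiplied by (1 − L_dar)/(1 − L_pbo), and again by a factor for the extra time. If L is larger on placebo, the first factor exceeds 1.

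**4. Illustration A: crude rate ratios.** No rate here comes from the documents. Assumptions: 1000 against 500 men; opioid hazard 0.003 per month before BPI-SF progression, multiplied by 2, 5 or 10 after it; placebo BPI-SF progression hazard 0.015 or 0.03 per month, hazard ratio 0.70; placebo median time on drug 15 months, hazard ratio 0.5; follow-up uniform over 12–45 months; 60 replicates.

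| Multiplier | Progression hazard | Lost, placebo | Lost, darolutamide | Ratio, full recording | Ratio, as written | Ratio, censored when recording stops |
|---|---|---|---|---|---|---|
| 2 | 0.015 | 19.3% | 8.8% | 0.963 | 1.101 | 1.026 |
| 2 | 0.03 | 30.1% | 14.7% | 0.944 | 1.167 | 1.031 |
| 5 | 0.015 | 30.7% | 16.6% | 0.910 | 1.117 | 1.042 |
| 5 | 0.03 | 39.0% | 23.3% | 0.894 | 1.148 | 1.017 |
| 10 | 0.015 | 38.2% | 20.9% | 0.856 | 1.117 | 1.043 |
| 10 | 0.03 | 45.2% | 25.7% | 0.813 | 1.141 | 1.011 |

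Check on the first row: (1 − 0.088)/(1 − 0.193) = 0.912/0.807 = 1.130, and 0.963 × 1.130 = 1.088. The remaining step to 1.101 is the extra opioid-free time. This illustration overstates the loss: it has no deaths, and it starts losses at BPI-SF progression itself, whereas an opioid begun before the documenting visit would still be recorded there.

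**5. Illustration B: both points allowed for.** Assumptions: 1000 against 500 men, 40 months' accrual, 48-month cut-off; hazard ratio 0.65 for stopping drug, BPI-SF progression and opioid start; placebo medians of 15–25 months to stopping, 24–40 months to BPI-SF progression and 60 months to opioid start before progression; opioid hazard 1–3 times higher afterwards; placebo median survival 44 months (the figure Protocol 1.1 cites from a denosumab trial), death hazard ratio 0.75; losses starting at the documenting visit. About 15–70 starts are lost, against about 20–102 without the two allowances. The hazard ratio moves towards 1 by about 0.03–0.04 in the mildest settings and 0.09 in the most severe.

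**The case against.** The strongest counter-argument is that the data may exist. Section 6.1.3 lists pain medications at follow-up contacts with no stop, the Synopsis follows opioid initiation to the end of the study, and SAP 6.1.4 expects follow-up opioid data. The CRF is not among the documents, nor is the supplementary document holding the sponsor's assessment of opioid treatments. A reader might infer that off-drug opioid starts after BPI-SF progression are never recorded. The documents do not support that; they support only that such starts need not be recorded. The counter-text does not remove the problem, because footnote 3, its SAP copy and Section 6.3.2.4 state the stop explicitly. Sites following different passages would collect different data.

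The stakes are also limited. The endpoint is not among the protocol's additional endpoints (Section 7.7.3), and SAP 6.2.3 treats its p-value as informative only. On-drug opioids are captured. In every illustrated setting the bias runs against darolutamide, so it would not create a false claim of benefit there. All of this stands and limits the severity.

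Finally, the size cannot be derived from the documents. The two illustrations differ materially: one crosses 1, the other gives a modest shift. That is a fair objection to quoting either as an estimate.

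**Conclusion.** Wrong as written: the Table 19 censoring rule does not match the collection schedule. An off-drug man who starts an opioid after BPI-SF progression can be carried as opioid-free to his last visit, and the protocol passages on whether recording continues conflict.

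Only time to first opioid use and the follow-up opioid table are affected. A reader might infer that the secondary pain endpoint is compromised too. It is not, because recording runs until that event; MFS is also untouched.

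The direction is conditional. If darolutamide delays both discontinuation and pain progression, the hazard ratio moves towards 1 or beyond. The magnitude depends on rates of discontinuation, BPI-SF progression, opioid start and death that the documents do not give, so the figures above are illustrations only. The change is worth making because it is cheap, but it bears on a supportive endpoint.

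**What to change.** 1. **Collection.** Reconcile the Synopsis, Table 4 footnote 3, Sections 6.1.3 and 6.3.2.4, and SAP Appendix 9.1. Keep the diary stop at pain progression, but record the start date of the first opioid at each existing follow-up contact until first opioid use or end of follow-up. Cost: one CRF item at contacts already made. It cannot recover starts that were not recorded.

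2. **Censoring.** In SAP Table 19, replace the date of the last visit with the last visit at which concomitant or pain medication was actually collected. Where collection followed footnote 3, this is the later of the end-of-study treatment visit and the visit of documented pain progression. The later date is needed because a man who progresses on BPI-SF while on drug still has all concomitant treatments recorded until his end-of-study treatment visit. Cost: one table row, with no new data.

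If only change 2 is made, the SAP should say that it gives up some follow-up and leaves informative censoring, since men are censored just as their opioid risk may rise. In illustration A it brings the ratio from 1.10–1.17 to 1.01–1.04, against 0.81–0.96 with full recording, so it removes only part of the bias. The follow-up opioid table should carry a note on how long opioid use was collected.

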6.1.1 Procedures during the screening period (-28 to -1 days)

A prospective study subject will receive both written and verbal information about the study, and will have an opportunity to ask questions and sufficient time to decide whether or not to participate in the study. The original signed and dated IC must be retained in the Investigator's study file and a copy must be provided to the patient.

All patients for whom the IC procedure is completed successfully will be assigned a subject number.

In addition to central laboratory sample collection, a local PSA value should be obtained at screening and used to confirm the patient has CRPC (inclusion criterion 4) and meets inclusion criterion 6.

To define CRPC and fulfil inclusion criterion 4, 3 subsequent PSA values rising after the nadir must be taken when the patient was on androgen deprivation therapy (ADT) that started at least 4 weeks before each PSA sampling, or at least 4 weeks after a bilateral orchiectomy.

PSA values used in calculation of PSADT should preferably have been obtained using the same assay, preferably at the same laboratory. PSADT should not be calculated using PSA values obtained when testosterone is rebounding after ADT (started at least 4 weeks before each PSA sampling, or at least 4 weeks after a bilateral orchiectomy). At least 3 PSA values need to be available and measured over the last 12 months before randomisation, at least 4 weeks apart. Screening PSA from local laboratory must be included in the PSADT calculation. The PSA values used for the calculation must be > 0.2 ng/ml and the screening value ≥ 2 ng/ml. The PSA values used for the calculation of PSADT will be recorded on the CRF.

PSADT will be calculated using a linear regression model of the normal logarithm of PSA and time ([Pound CR et al., 1999](#)). Medical monitor must review the PSA and PSADT values submitted on the eligibility form before randomisation.

Patient screening must occur within 28 days before the first study treatment dosing at visit 1 (day 1). For practical reasons, screening procedures can be performed on separate occasions during the screening period. Re-testing is allowed during the 28-day window only, if there is a medical or logistical reason. Re-testing of the safety laboratory assessments, testosterone and PSA may be allowed after consulting with the medical monitor. It is estimated that it will take 7 to 14 days to obtain results from the safety laboratory assessments, testosterone and PSA (including PSADT).

Screening procedures that fall outside of the 28-day window must be repeated. Re-screening of a patient who did not fulfil the eligibility criteria is allowed after at least 30 days from last screening decision. If a patient is re-screened, a new screening number will be allocated and a link will be made between the screening numbers of the same patient. Only one re-screening for each patient is allowed, after consultation with medical monitor.

The following procedures will be performed during the screening period:

- Signed and dated IC
- An optional PG IC signed and dated at screening (or later during the study if feasible) for pharmacogenetic research study unless precluded by local guidelines, e.g. IEC/IRB or regulatory authorities.
- FACT-P, EORTC-QLQ-PR25 and EQ-5D-3L questionnaires
- Demographic data (date of birth, age, racial group)
- Medical history and current medical condition
- Prostate cancer history including prior treatments and procedures
- Physical examination including weight and height
- A triplicate 12-lead ECG in a supine position after at least 10 minutes rest. The 3 consecutive recordings will be performed within approximately 5 minutes. An ECG with a QTcF > 500 ms should be confirmed by a second ECG taken 1-2 hours later.
- BP and HR (unless recorded by ECG) in a supine position after at least 10 minutes rest.
- ECOG performance status
- Laboratory safety assessments (haematology, chemistry and urinalysis), testosterone, and PSA.
- Chest, abdomen and pelvic CT or MRI **and** bone scan.

CT/MRI and bone scans performed within 42 days prior to start of study treatment are acceptable as screening scans. A local qualified site physician (e.g. site radiologist or PI, at the PI's discretion) must first review the screening scans and confirm the patient is non-metastatic before submitting the scans to central review to confirm eligibility. If the local qualified site physician detects metastasis, the scans should not be submitted to central review.

- AEs and concomitant treatments
- Dispensing pain diary

6.1.2 Procedures during the study treatment period

PK assessments at study centres participating in PK sample collection are described in Section 6.2.

6.1.2.1 Day 1 (visit 1)

The patient will arrive at the study centre in the morning of day 1. The first study treatment will be administered with breakfast at the study centre. The following procedures will be performed before administration of study treatment:

- Confirmation of the patient's eligibility
- The patient will be randomised using IRT. In case the start of study treatment is not logistically feasible on the same day as randomisation, randomisation can be performed 1 day before the initiation of study treatment.
- BPI-SF, FACT-P, EORTC-QLQ-PR25 and EQ-5D-3L questionnaires
- Physical examination including weight
- A triplicate 12-lead ECG in a supine position after at least 10 minutes rest. The 3 consecutive recordings will be performed within approximately 5 minutes. An ECG with a QTcF > 500 ms should be confirmed by a second ECG taken 1-2 hours later.
- BP and HR (unless recorded by ECG) in a supine position after at least 10 minutes rest.
- Laboratory safety assessments (haematology, chemistry, and urinalysis), testosterone, and PSA
- A blood sample for DNA extraction taken from patients who have signed the PG IC (or later during the study if feasible) unless precluded by local guidelines, e.g. IEC/IRB or regulatory authorities
- A blood (plasma) sample for tumour-related biomarker analysis unless precluded by local guidelines, e.g. IEC/IRB or regulatory authorities (see Section 6.5)
- Current medical condition, AEs and concomitant treatments
- Study drug will be dispensed for 28 days and accountability performed
- Collection of pain diary

Patients will continue taking study treatment at home throughout the study treatment period.

